Part 3 (Dose Finding) will follow a Bayesian optimal interval (BOIN) design to guide dose-escalation and de-escalation decisions based on the cumulative number of subjects experiencing a DLT at the current dose level. Table 2 gives the dose levels of venetoclax in combination with oral AZA to be explored. Venetoclax and oral AZA may be administered for up to 24 cycles.

In the dose-escalation portion, each dose level will initially enroll at least 6 DLT-evaluable subjects. The first cohort of subjects will be assigned to receive dose Level 1 (venetoclax [400 mg] QD on Days 1 to 21 in combination with oral AZA [200 mg] QD on Days 1 to 14 of each 28-day cycle) with dose escalation or de-escalation for the subsequent cohort of subjects guided by a BOIN design. Table 3 gives the BOIN

dose-escalation decision rule for a target toxicity rate of 20% and optimal interval of (16.9%, 25.1%). Approximately 12 subjects will be assigned to receive the preliminary RPTD identified during dose escalation.

The safety expansion portion will enroll at least 12 additional subjects to receive venetoclax in combination with oral AZA at the preliminary RPTD identified from dose-escalation portion of Part 3.

Subjects will be assessed for potential evidence of AML relapse through medical history, physical examination, and hematological laboratory review as detailed in the Operations Manual Section 3.14.

Subjects with controlled disease who have not experienced a DLT and who have tolerable side effects may continue to receive study drugs for 24 cycles or until relapse or unacceptable toxicity occurs. The investigator may discontinue a subject from the study as deemed appropriate.

Subjects who discontinue study drug but have not had an event of documented relapse will return for post-treatment follow-up visits. Subjects in Part 3 (Dose Finding) will return for post-treatment follow-up visits every 3 months (± 28 days) for 1 year and then every 6 months (± 28 days) thereafter starting from study drug discontinuation until documented relapse or the study ends, whichever occurs first. After relapse, survival information will be collected (e.g., via telephone calls and/or clinical visits) every 3 months (± 28 days) or more frequently at the sponsor's discretion for up to 2 years after relapse or until the sponsor's decision to stop follow-up.

Table 2. Venetoclax and Oral AZA Dose Levels

| Dose Level | Venetoclax Dose | Oral AZA Dose |

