5.7 Study Drug

Study drugs refer to drugs that are used (or can be used) in this study to assess the safety and the efficacy of the Investigational Product. Investigators will assess the relationship of AEs to the use of study drugs (see Table 5 for the list of study drugs).

Venetoclax manufactured by AbbVie will be administered orally, QD for each 28-day cycle beginning on Day 1 for subjects in Part 1 (Dose Confirmation) and Part 3 (Dose Finding).

If vomiting occurs after taking venetoclax, another dose should not be taken that day. In cases where a dose of venetoclax is missed or forgotten, the subject should take the forgotten dose as soon as possible, provided that the dose is taken within 8 hours of the missed dose and is taken with food and water. Otherwise, the missed dose should not be taken and the subject should take the next dose at the next scheduled dosing time.

AZA will be administered SC or IV, QD on Days 1 to 5 of each 28-day cycle, for up to 6 cycles (refer to Operations Manual Section 6.1) for subjects in Part 1. AZA must be prepared and administered by the route indicated in the package insert, prescribing information, local SmPC, or equivalent.

Oral AZA will be administered QD on Days 1 to 14 of each 28-day cycle for up to 24 cycles for subjects in Part 3. Subjects will be trained to self-administer oral AZA (refer to Operations Manual Section 6.1).

If vomiting occurs after taking oral AZA, a second dose should not be taken that day as subjects must not take 2 doses on the same day.

In cases where a dose of oral AZA is missed or forgotten, the subject should take the forgotten dose as soon as possible and resume the normal schedule in the following day.

The investigational medicinal products for this study are venetoclax, AZA, and oral AZA. AbbVie will supply venetoclax, AZA, and oral AZA. AbbVie-provided study drug should not be substituted or alternately sourced unless otherwise directed by AbbVie. AbbVie will not supply drugs other than venetoclax, AZA, and CC486. Non-investigational medicinal product (i.e., BSC) must be obtained commercially. AbbVie will not provide or reimburse for treatments administered for BSC.

If a subject is unable to come to the study site to pick up their study drug due to COVID-19, a direct-to-patient (DTP) study drug shipment can be made from the study site to the subject if allowed by local

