6.3 Dose-Limiting Toxicity Criteria

Part 1 (Dose Confirmation) and Part 3 (Dose Finding)

Any of the following events during Cycle 1, which are considered possibly or probably related to the administration of venetoclax, will be considered a DLT:

- Hematologic toxicities
 - any Grade ≥ 3 neutropenia lasting more than 7 days
 - any Grade ≥ 3 thrombocytopenia lasting more than 7 days
- Nonhematologic toxicities
 - any Grade 3 AE lasting ≥ 72 hours except for Grade 3 hypersensitivity reactions or Grade 3 localized injection-site toxicities
 - Grade ≥ 3 nausea, diarrhea, or vomiting despite adequate/maximal medical intervention lasting more than 7 days (Part 3 only)
 - any Grade ≥ 4 AE
 - any Hy's law cases defined as elevated aspartate aminotransferase (AST) or alanine aminotransferase (ALT) ≥ 3 × ULN with concurrent elevated total bilirubin ≥ 2 × ULN in the absence of elevated alkaline phosphatase or other conditions that could cause these laboratory abnormalities

In addition, AEs not meeting above criteria but lead to omitting > 20% of the scheduled dose within the cycle should be considered as a DLT unless clearly related to underlying disease.

Treatment delay due to toxicity lasting greater than 14 days since the last dose of venetoclax will also be considered DLT.

Any DLT will require an interruption and possible discontinuation of venetoclax or AZA. Venetoclax may be reintroduced at a reduced dose if the toxicity grade returns to ≤ Grade 1 or to baseline if Grade 2 at study entry. If the subject is considered to be acceptable for resumption of venetoclax dosing at the same dose or reduced dose on Day 7 of the dose interruption, the event should not be designated as a DLT.

To be considered DLT-evaluable in Part 3, subjects must complete at least 80% of assigned venetoclax dosing and oral AZA dosing in Cycle 1 or experience a DLT in Cycle 1.

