APPENDIX D. RECOMMENDED DOSE REDUCTIONS RELATED TO DRUG TOXICITIES

Recommended Venetoclax/Azacitidine and Venetoclax/Oral AZA Dose Modifications for Toxicities

| Event | Occurrence | Action | | |
|--|--|---|--|--|
| Nonhematologic Adverse Eve | Nonhematologic Adverse Events ^a | | | |
| ≥ Grade 3 nonhematologic toxicities | 1 st occurrence | Interrupt venetoclax + AZA or venetoclax + oral AZA. Once the toxicity has resolved to Grade 1 or baseline level, venetoclax + AZA or venetoclax + oral AZA may be resumed at the same dose. No dose modification is required. | | |
| | 2 nd and subsequent occurrences | Interrupt venetoclax + AZA or venetoclax + oral AZA. Follow dose reduction guidelines in Section 6.2 when resuming treatment with venetoclax + AZA or venetoclax + oral AZA after resolution. A greater dose reduction may occur at the discretion of the investigator after discussion with TA MD. | | |
| ≥ Grade 3 diarrhea (Part 3 only) | 1 st occurrence | Interrupt venetoclax + oral AZA and provide adequate/ maximum medical intervention (refer to Appendix F). Resume venetoclax + oral AZA at same dose when toxicity resolves to ≤ Grade 1. | | |
| | 2 nd and subsequent occurrences | Interrupt venetoclax + oral AZA. Follow dose reduction guidelines in Section 6.2 when resuming venetoclax + oral AZA after resolution. A greater dose reduction may occur at the discretion of the investigator after discussion with TA MD. | | |
| ≥ Grade 3 nausea and/or vomiting (Part 3 only) | 1 st occurrence | Interrupt venetoclax + oral AZA and provide adequate/maximal medical intervention. Resume venetoclax + oral AZA at same dose when toxicity resolves to ≤ Grade 1. | | |
| | 2 nd and subsequent occurrences | Interrupt venetoclax + oral AZA. Follow dose reduction guidelines in Section 6.2 when resuming venetoclax + oral AZA after resolution. A greater dose reduction may occur at the discretion of the investigator after discussion with TA MD. | | |

| Event | Occurrence | Action |
|--|---|--|
| Hematologic Toxicities ^{a,b} | | |

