| Grade 3 neutropenia and/or thrombocytopenia if lasts 7 days or longer; or Grade 3 neutropenia with infection or fever; or Grade 3 thrombocytopenia with hemorrhage; or | 1 st occurrence | Interrupt venetoclax + AZA or venetoclax + oral AZA. Treatment may be resumed at the same dose once the condition(s) have improved or have been stabilized with adequate treatment (anti-infective therapy, transfusions, or growth factors) and toxicity has resolved to ≤ Grade 1 or has returned to 75% of the baseline level, as assessed by investigator. Dose interruption in case of prolonged toxicity (≥ 14 days) should be discussed with the TA MD. Any dose reduction should be discussed with the TA MD when resuming treatment with venetoclax + AZA or venetoclax + oral AZA after resolution. |
| All Grade 4 hematologic toxicities (except lymphopenia) | 2 nd and subsequent occurrence | Interrupt venetoclax + AZA or venetoclax + oral AZA. Follow dose reduction guidelines in Section 6.2 when resuming treatment with venetoclax + AZA or venetoclax + oral AZA after resolution (resolved to ≤ Grade 1 or returned to 75% of the baseline level as assessed by investigator). Additional dose reductions may occur at the discretion of the physician and in consultation with the TA MD. |
| Consider discontinuing veneto 2 weeks. | clax for subjects w | ho require dose reductions to less than 100 mg for more than |

AZA = azacitidine; TA MD = Therapeutic Area Medical Director

- a. Once a dose has been reduced, the dose will not be increased again.
- b. There is no increase in oral AZA dose independent of percentage of blasts in the bone marrow.

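### Protocol 6.3 classifies a Cycle 1 toxicity hold ending on Day 7 both as a DLT and as not a DLT; on the second reading the Part 3 subject drops out of Table 3

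*Protocol*

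**What the plan says.** DLTs are the primary endpoint of Part 3 (Protocol 3.1). Three rules in Section 6.3 bear on a Cycle 1 toxicity hold.

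- **Omission rule.** For AEs outside the listed DLT criteria, the rule is that those which "lead to omitting > 20% of the scheduled dose within the cycle should be considered as a DLT unless clearly related to underlying disease".
- **Day-7 sentence.** If the subject is judged fit to restart venetoclax, at the same or a reduced dose, "on Day 7 of the dose interruption, the event should not be designated as a DLT". No grade limit is attached.
- **Part 3 evaluability.** To count, "subjects must complete at least 80% of assigned venetoclax dosing and oral AZA dosing in Cycle 1 or experience a DLT in Cycle 1".

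Section 4.1 says that "each dose level will initially enroll at least 6 DLT-evaluable subjects", and Table 3 sets escalation by the number of DLTs among DLT-evaluable subjects. Appendix D recommends holds of both drugs. For a first nonhematologic toxicity of Grade 3 or higher the action begins "Interrupt venetoclax + AZA or venetoclax + oral AZA. Once the toxicity has resolved to Grade 1 or baseline level". Its hematologic triggers include "Grade 3 neutropenia and/or thrombocytopenia if lasts 7 days or longer" and Grade 4 hematologic toxicity other than lymphopenia.

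Nothing else settles the order of the rules. Protocol Section 7 gives no DLT analysis. The supplied SAP was written for protocol version 2.0, has no Part 3 and contains no DLT rule.

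**The concern.** The omission rule and the Day-7 sentence can apply to the same event and give opposite answers on the primary endpoint. Which one was applied decides whether the subject is an evaluable DLT or is absent from the escalation table altogether. In the second case a subject who lost dosing because of toxicity contributes to neither the numerator nor the denominator of the rate used to select the RPTD.

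A separate question arises because the Day-7 sentence has no grade limit. Read literally, it also cancels listed DLTs, such as Grade 4 or higher AEs or prolonged Grade 3 cytopenia, whenever restart on Day 7 is acceptable.

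The 46 Part 3 subjects had been enrolled by September 2022, so the dose assignments look settled. What remains open is the final DLT classification and how firmly the RPTD is supported.

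**Working it through.** **1. Table 3 reproduces.** Inputs from Section 4.1: target 20%, interval (16.9%, 25.1%). Escalate if x/n ≤ 0.169; de-escalate if x/n ≥ 0.251; eliminate if P(p > 0.20 | x, n) > 0.95. The Beta(1,1) prior and the 0.95 cutoff are assumed, because the protocol states neither. All nine columns (n = 6 to 14) match. The table is sound; the question is what is fed into it.

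**2. Share of venetoclax omitted.** Scheduled days come from Table 2. Restarting on Day 7 of the hold means 6 missed doses; holding seven full days means 7. Held days are assumed not to be made up, since dosing is tied to fixed cycle days (Section 4.1, Appendix H). Omitted share = missed / scheduled.

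| Venetoclax schedule | Part 3 level | 6 missed | 7 missed | Completed (6 / 7 missed) |
|---|---|---|---|---|
| 21 days | 1 and 2 | 6/21 = 28.6% | 33.3% | 71.4% / 66.7% |
| 28 days | 3 | 6/28 = 21.4% | 25.0% | 78.6% / 75.0% |
| 14 days | -1 | 6/14 = 42.9% | 50.0% | 57.1% / 50.0% |

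Every omitted share exceeds 20%, so the omission rule says DLT. Every completed share is below 80%, so a subject exempted by the Day-7 sentence is not evaluable.

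**3. When the hold must start.** More than 20% is first reached at 5 of 21 doses (23.8%), 6 of 28 (21.4%) or 3 of 14 (21.4%). A hold ending on Day 7 reaches that if it starts by Day 17, 23 or 12 respectively. One day later, the missed doses inside the schedule are 4/21 = 19.0%, 5/28 = 17.9% or 2/14 = 14.3%, and venetoclax omission does not trigger the conflict. If oral AZA is held too, 3 of its 14 days already leaves 78.6%, below the evaluability limit.

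**4. Effect on Table 3.** Compare one hold counted as a DLT (x/n) with the same subject excluded, (x − 1)/(n − 1), or replaced by a subject without a DLT, (x − 1)/n.

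| Counted as DLT | Excluded | Replaced |
|---|---|---|
| 2/7 de-escalate | 1/6 escalate | 1/7 escalate |
| 2/8 to 2/11 stay | 1/7 to 1/10 escalate | 1/8 to 1/11 escalate |
| 3/9 to 3/11 de-escalate | 2/8 to 2/10 stay | 2/9 to 2/11 stay |
| 3/12 stay | 2/11 stay | 2/12 escalate |
| 4/12 de-escalate | 3/11 de-escalate | 3/12 stay |

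At n = 12 without replacement, only elimination changes (5/12 eliminate, 4/11 de-escalate).

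**5. Illustrative size.** Let a be the rate of other DLTs and b the rate of these holds. Both are assumed; neither is in the documents. The rate is a + b if holds count, a/(1 − b) if they are excluded, and a if they stay in as non-DLTs. The chance of an escalate action at n = 6 is (1 − q)^6 + 6q(1 − q)^5, with q the relevant rate.

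| a, b | Counted | Excluded | Kept as non-DLT | P(escalate), counted | P(escalate), excluded |
|---|---|---|---|---|---|
| 15%, 5% | 20% | 15.8% | 15% | 66% | 76% |
| 15%, 10% | 25% | 0.15/0.90 = 16.7% | 15% | 53% | 74% |
| 15%, 15% | 30% | 0.15/0.85 = 17.6% | 15% | 42% | 71% |

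**The case against.** The strongest reply is that there is no contradiction. The Day-7 sentence follows the criteria and says an event should not be designated a DLT, which presupposes one that would otherwise qualify. It can be read as a deliberate exception: toxicity that permits restart within a week is not dose-limiting. That reading is available, and 6.3 should then say so. It would leave the omission rule little to do beyond longer holds or several short holds that add up, and it would extend to Grade 4 events without stating that this is intended.

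Four further points stand.

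- The omission rule covers only AEs outside the listed criteria and not clearly due to the disease. Many Appendix D triggers are, or become, listed DLTs. For those the tension is between the listed criteria and the Day-7 sentence, not with the omission rule.
- A reader might infer that the 80% rule is what lowers the DLT rate. It is not. The exemption takes the event out of the numerator; excluding the subject then raises the rate slightly compared with keeping a non-DLT (17.6% against 15.0% in the last row of step 5). The rate is too low only if these holds ought to count.
- The frequency of such holds is unknown. Appendix D is a recommendation, Section 6.2 says treatment may be withheld, and restart depends on recovery, so they may be few.
- Redefining the primary endpoint of an open-label study after the Cycle 1 data exist would itself be post hoc.

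**Conclusion.** Section 6.3 gives opposite classifications of one primary-endpoint event, at every Part 3 dose level, with no stated precedence. If the Day-7 sentence governs, the affected subject is in neither part of the Table 3 rate, and a single subject can change the action. This rests on the hold falling within dosing days (start by Day 17, 23 or 12), on held doses not being made up, and on the AE not being clearly related to underlying disease. The probabilities in step 5 are illustrations under assumed rates, not estimates for this trial.

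Part 1 has the same conflict between the two sentences but no 80% rule, so an exempted subject there would not be excluded on that ground.

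A reader might go further and infer that the RPTD is too high, or that it must be withdrawn if a stricter count crosses a Table 3 limit. The documents support neither. They give no count of holds and do not say which sentence was applied during escalation, and Table 3 is an escalation rule, not a stated criterion for the final RPTD. If no such hold occurred, nothing changes.

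**What to change.** 1. State in 6.3 which sentence governs. Add that the Day-7 exemption does not cancel the more-than-20% omission rule or, unless a clinical justification is given, Grade 4 or higher events.
2. State that a Part 3 subject whose Cycle 1 dosing fell below 80% because of a related AE is DLT-evaluable.
3. Before database lock, list every Part 3 Cycle 1 toxicity hold with its start day, doses missed of each drug, and classification. Report DLT rates by dose level twice: under the classification used during escalation, and with these holds counted as DLTs. If the two lead to different rows of Table 3, discuss what that means for the RPTD.

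The stricter count should be a sensitivity analysis, not an automatic replacement of the RPTD. Protocol 7.1 leaves the SAP to be finalized before database lock, so items 2 and 3 can be set out there. The work is a re-tabulation of AE and dosing records already collected, in 46 subjects. The downside is a possibly less favourable DLT rate, because short, recoverable holds would count in the second tabulation.

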7 STATISTICAL METHODS & DETERMINATION OF SAMPLE SIZE

7.1 Statistical and Analytical Plans

The statistical methods provided in this protocol will be focused on primary and key secondary analyses. Complete and specific details of the statistical analysis will be described and fully documented in the Statistical Analysis Plan (SAP). The SAP will be finalized prior to the database lock.

7.2 Definition for Analysis Populations

The treated population includes all enrolled subjects who received at least one dose of both venetoclax and AZA in Part 1, as well as all subjects who received at least one dose of both venetoclax and oral AZA in Part 3. Unless otherwise noted, the treated population will be used for all safety, efficacy, and baseline analyses.

7.3 Statistical Analyses for Efficacy

Efficacy Analyses

Relapse Free Survival

RFS is the time from drug assignment to the date of relapse or the date of death from any cause, whichever comes first. If a subject does not experience an RFS event, the subject's data will be censored at the date of the subject's last disease assessment date (e.g., last bone marrow or hematology laboratory date) or date of drug assignment if the subject does not have any postbaseline disease assessment. The distribution of RFS will be estimated using Kaplan-Meier methodology.⁴⁴

Overall Survival

OS is defined as time from drug assignment to death from any cause. OS data from subjects who have not died will be censored at the last known alive date. The distribution of OS will be estimated for each study arm using Kaplan-Meier methodology.⁴⁴

MRD Conversion Rate

The MRD conversion rate is defined as the proportion of subjects deemed MRD-positive ($\geq 10^{-3}$) at screening who convert to MRD < 10⁻³ after drug assignment. Subjects who are MRD < 10⁻³ at screening

will be excluded from the analysis. The MRD conversion rate (95% CI) will be estimated using binomial distribution (Clopper-Pearson exact method).⁴⁵

Time to Deterioration in GHS/QoL Score

Time to deterioration in GHS/QoL score is defined as time from drug assignment to death from any cause, or the first-time decrease of ≥ 10 points from baseline, whichever occurs first.⁴⁶ Subjects without any of the specified events will be censored at subject's last EORTC QLQ-C30 assessment. The distribution of time to deterioration in GHS/QoL will be estimated using Kaplan-Meier methodology.⁴⁴

Change in Global Fatigue Score from Baseline to Post baseline

Fatigue will be assessed using the global fatigue score as measured by PROMIS Fatigue SF 7a. Scores will be computed according to the PROMIS fatigue scoring manual. Descriptive summaries will be provided for the change in fatigue score from baseline to post-baseline visits. Subjects without baseline score or any postbaseline score will be excluded from the analysis.

Additional Efficacy Analyses

Details on other efficacy analyses (i.e., analysis based on ELN⁴⁷ criteria if data are available) are provided in the SAP.

7.4 Statistical Analyses for Safety

Safety analyses will only include subjects in the Safety Analysis Set as defined in Section 7.2.

Analysis of Adverse Events

Treatment-emergent AEs will be summarized by preferred terms within a System Organ Class according to the Medical Dictionary for Regulatory Activities (MedDRA). In addition, the percentage of subjects experiencing an AE at a given NCI CTCAE (version 5.0) toxicity grade and relationship to study drug will be provided. Treatment-emergent SAEs will be summarized similarly.

Analysis of Laboratory Data

Change from baseline will be analyzed for each scheduled postbaseline visit for blood chemistry and hematology parameters. Subjects who do not have a baseline measurement or do not have any postbaseline measurement will not be included.

Where it is applicable, blood chemistry and hematology laboratory determinations will be categorized according to the NCI CTCAE. Grades and shifts from baseline NCI CTCAE grades to maximum postbaseline grades will be assessed.

7.5 Multiplicity Adjustment and Overall Type I Error Control

Not applicable for this study.

7.6 Sample Size Determination

Part 1

The sample size for Part 1 is intended to provide an adequate safety evaluation. The probability of observing at least 1 AE in a cohort of 20 subjects for various true AE rates is provided in Table 9.

Table 9. Probability of Observing at Least One Adverse Event in a Cohort of 20 Subjects for Various True Adverse Event Rates

| True AE Rate | Probability to Observe at Least 1 AE |
|--------------|--------------------------------------|
| 0.05 | 0.64 |
| 0.10 | 0.88 |
| 0.15 | 0.96 |
| 0.20 | 0.99 |

AE = adverse event

Part 3 (Dose Finding)

The total sample size for Part 3 (Dose Finding) will depend on the DLTs observed during dose escalation in Cycle 1 and is intended to provide an adequate safety evaluation of the RPTD of venetoclax in combination with oral AZA. Approximately 24 subjects will be assigned to receive the RPTD of venetoclax in combination with oral AZA. The probability of observing at least 1 AE in a cohort of 24 subjects for various true AE rates is provided in Table 10.

Table 10. Probability of Observing at Least 1 Adverse Event in a Cohort of 24 Subjects for Various True Adverse Event Rates

| True AE Rate | Probability to Observe at Least 1 AE |
|--------------|--------------------------------------|
| 0.05 | 0.71 |
| 0.10 | 0.92 |
| 0.15 | 0.98 |
| 0.20 | > 0.99 |

AE = adverse event

